### *Rationale for Group Therapy*

Since the beginning of the HIV/AIDS epidemic, many psychotherapies for PLH have been preferentially delivered as groups because of enhanced cost-effectiveness and the group format’s unique clinical benefits with respect to the enhancement of social support in a population suffering high rates of isolation and loneliness [23].

The theoretical basis of the original Spring Grove approach to treating existential distress in palliative care patients was that patients suffer extreme *isolation* because of their disease, and that psychedelic-assisted psychotherapy could help relieve this isolation by facilitating: 1) living meaningfully in the present moment, and 2) reaching out and authentically connecting with loved ones [22]. Various clinical benefits were reported from their uncontrolled experimental sessions, including improvements in mood and anxiety, and increased openness to communication with loved ones [119]. These older findings are consistent with more recent social psychology findings that psilocybin decreases the subjective feeling of social exclusion [120] and another classic psychedelic, LSD, enhances emotional empathy and prosocial behavior [121].

The Spring Grove team concluded that optimal clinical outcomes were dependent upon attaining a “psychedelic peak experience,” which was conceived of as akin to William James’ “conversion experience,” [122] or Abraham Maslow’s “peak experience,” [123] —a transcendent state of unity, intense positive emotions, and ineffability that was experienced as deeply meaningful. [22] To describe this mental state, the current psilocybin literature has adopted the terminology of the “complete mystical experience,” which is defined by standard criteria using a validated psychometric measure, the Mystical Experience Questionnaire—30 item [124]. Because the Spring Grove team believed that the “transcendental nature of the experience [could] neutralize a sense of alienation...” they sought to facilitate such experiences in order “to maximize patients’ opportunities for living by lessening their sense of isolation and alienation, and in so doing, assist in their reaching out to those around them” [125]. One aspect of this model that has received little mention in the recent literature is that the original Spring Grove protocol included non-drug *family therapy sessions* conducted both before and after drug sessions [22]. The purpose of these sessions was to prepare the family to better help the patients integrate their psychedelic experience after the drug sessions, as well as to aid the family in their imminent grieving process.

Spontaneous feedback from several subjects in the recent NYU psilocybin-assisted psychotherapy trial for existential distress in cancer patients included the request to be introduced to the other study subjects [19], apparently to share, process and integrate their experiences in a setting of mutual aid and understanding. Subjects from recent MDMA-assisted psychotherapy trials for PTSD have also spontaneously made this request, leading the study

sponsors to create a web forum for the patients to be in touch with each other after completing the trials [126]. It appears to be helpful to patients treated with psychedelic-assisted psychotherapy to spend time with peers in their attempt to integrate the “peak” experiences, the phenomenology of which can be rather uncanny and perhaps difficult for psychedelic-naïve family or friends to comprehend [127].

Conducting non-drug psychotherapy sessions in groups may shed light on possible key mechanisms of psilocybin-assisted psychotherapy for existential distress. Whereas *therapeutic alliance* is thought to be the most important mediator of clinical outcomes in individual psychotherapy, *group cohesion* is widely recognized as the analogous mechanism in group psychotherapy [128, 129]. Examining the change of group cohesion pre- and post-psilocybin with validated self-report [130] and observer-rated instruments [131] will provide a novel and standardized means of observing how psilocybin drug sessions may affect the interpersonal functioning of distressed palliative care patients.

A significant limitation of group therapy clinical trials is that large sample sizes are required to demonstrate efficacy because of the likely interdependence of outcomes of members of the same group [132]. For this reason, qualitative (e.g. Interpretive Phenomenological Analysis) and/or sequential (e.g. the Hill Interaction Matrix) measures of psychotherapeutic *process* are often used to make inductive inferences about clinical change from group therapy over time [133]. Process is understood as the conglomeration of intrapersonal functions, interpersonal dynamics and group environment that leads to therapeutic change [134]. To improve the evidence base for group psychotherapy, the American Group Psychotherapy Association (AGPA) has developed clinical practice guidelines [135] and a standard set of measures and tools for creating and managing psychotherapy groups for clinical practice and research [136]. In developing the protocol for this proposed study, we have drawn not only from the literatures on psilocybin-assisted psychotherapy and palliative care, but also from these AGPA clinical and research guidelines, as well as on the consultation of local group psychotherapy experts [137].

#### *Rationale for Dosing Regimen*

Griffiths et al [138] have characterized the dose-response relationship of oral psilocybin in healthy volunteers. They found that when considering the odds of attaining a complete mystical experience versus having a temporary anxiety reaction during the drug experience (lasting on the order of minutes), the optimal dose likely falls between 0.29mg/kg and 0.43mg/kg [138]. This dose range has been successfully used in studies of psilocybin-assisted psychotherapy for existential distress in cancer patients [19, 20], severe alcohol use disorder [107] and tobacco use disorder [108]. The current study will employ a dose of 0.3mg/kg po in the first group, and if this is well tolerated will then escalate to 0.36mg/kg po in subsequent groups.

The dosing of the psychotherapy—8 weekly sessions—was chosen on the basis of comparison with similar group psychotherapies for existential distress in palliative care patients. The group psychotherapy with the best evidence-base for treating existential distress in palliative care patients, Meaning-Centered Group Psychotherapy, also employs 8 sessions [139]. The group psychotherapy with the best evidence-based for treating complicated grief has 16 weekly sessions [140]. Our protocol uses a modified course of Brief Supportive-Expressive Group Therapy, which was designed and tested as a 12-week course of treatment [76]. Empirical data suggest that group therapies lasting at least 12 sessions are shown to have greater correlations between group cohesion and clinical outcomes [129]. We hypothesize that psilocybin will catalyze group cohesion in a shorter period of time, thus making 12-16 weeks of group therapy unnecessary for detecting comparable results with regards to cohesion and clinical outcomes.

#### *Rationale for Supportive-Expressive Group Therapy*

While prior trials of psilocybin-assisted psychotherapy for existential distress in palliative care patients have followed a standard drug administration safety protocol, they have not used manualized psychotherapies in the non-drug therapy sessions; our study will be the first to do this, which should enhance generalizability of the results. The format and content of SEGT are appropriately flexible for incorporating individual psilocybin sessions during the course of therapy, and including psychoeducation on psilocybin in the preparatory sessions. The focus of SEGT on expressing emotions and enhancing communication with caregivers is expected to be helpful in integrating psilocybin experiences [118]. Psilocybin has been shown to enhance access to positive emotional memories [141] and to increase the personality trait of openness [106], and this should support SEGT's aim of increasing awareness of one's emotions and openness to new experiences. Because the primary aim of this pilot trial is to assess safety and feasibility of this modality—and assessing efficacy is a secondary aim—no control group of traditional SEGT will be included in the study. For the rationale on why psilocybin monotherapy (without an adjunctive psychotherapy) will not be offered as control condition, see above.

## 1.4 Study Hypotheses

### Primary

1. The study will recruit, consent and enroll at least 18 subjects (in 3 groups of 6 members) over 18 months; these subjects will complete all treatment and evaluation sessions and they will experience no treatment-emergent serious adverse events.

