Safety Assessments	Adverse events Vital signs  Adverse Event Medication Session Form  Columbia Suicide Severity Rating Scale  Community Observer Rating Form
Feasibility Assessments	Rate of Patient Recruitment Rate of Patient Retention (Sessions Attended and Follow-ups Completed) Client Satisfaction Scale Individual Patient and Important Other/Caregiver Interviews Supportive-Expressive Group Therapy Topic Grid Focus Groups with Patients and Important Others/Caregivers
Primary Outcomes	Demoralization Scale-II Inventory of Complicated Grief
Secondary Outcomes	Antiretroviral Medication Adherence Scale Alcohol Use Disorders Identification Test Center for Epidemiologic Studies Depression Scale—Revised Challenging Experience Questionnaire Clinical Global Impressions Scale Credibility/Expectancy Questionnaire Duke/UNC Functional Social Support Questionnaire—5 Drug Use Disorders Identification Test Experiences in Close Relationships scale—Modified 16 Group Psychotherapy Intervention Rating Scale Group Questionnaire HIV and Abuse Related Shame Inventory Individual Group Member Interpersonal Process Scale International Personality Item Pool—Openness to Experience-20 McGill Quality of Life Questionnaire—Revised-Short Multidimensional Assessment of Interoceptive Awareness—Revised Mystical Experience Questionnaire—30 Nature Relatedness Scale, Short Form Post-traumatic Growth Inventory—Short Form PTSD Checklist-5 Schedule of Attitudes towards Hastened Death Social Connectedness Scale-Revised

	State-Trait Anxiety Inventory Qualitative analysis of therapy sessions, interviews & focus groups
--	--

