#### *LTAS – An Ideal Model for Studying Chronic Existential Distress in Palliative Care Patients*

Clinical trials in palliative care are fraught with many methodological challenges, especially subject recruitment given patients’ lack of interest in spending their limited time in research studies, or inability to comply with the physical demands of attending study visits and research protocols [113]. Attrition rates of up to 50% are not uncommon among psychotherapy trials with palliative care patients [77, 114, 115]. Recent trials of psilocybin-assisted psychotherapy for existential distress in cancer patients have struggled with recruitment [28]. The current proposed study of psilocybin-assisted psychotherapy in LTAS is unlikely to be hindered by these same recruitment challenges because the form of existential distress to be examined, demoralization, is thought to occur at high rates [65] among a largely ambulatory population that is known to avidly volunteer for medical research [116] and is desperately in search of treatment options [65]. Despite the fact that HIV is now considered a “chronic illness” and not an acutely life-threatening condition for most patients, PLH potentially face their mortality on a daily basis when they choose, or choose not, to adhere with their ART regimen, thus likely enhancing existential distress chronically.

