### 3.2 Number of Subjects

We estimate that a total of 60 patients will be screened in-person for the study. We estimate that at least 18 patients will need to be enrolled given the high rate of drop outs seen in group psychotherapy studies in this population [114]. Patients who have been assigned to a group will be replaced only if they drop out prior to the first group therapy session (this avoids the possible symbolic message that if a subject were to die, that he would be easily replaced in the group). We aim for, at minimum, 8 subjects (two groups of at least 4 subjects each) will complete the study; at maximum, 36 subjects (six groups of six subjects each) will complete the study. (See Section 8.2.1 Sample Size and Power Estimate.)

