### **8.2 Determination of Sample Size and Accrual Rate**

#### **8.2.1 Sample Size and Power Estimate**

This pilot study of the safety and feasibility of psilocybin-assisted group therapy aims to enroll at least 18 subjects, and will have a maximum total sample size of 36. We estimate needing to enroll 18 subjects given attrition rates of up to 45% reported in trials of other group therapies for existential distress in palliative care patients [114]. For comparison, four different safety and feasibility pilot studies of psilocybin-assisted psychotherapy have been conducted over the last two decades, and have included 9, 10, 12 and 15 patients each [18, 107, 108, 110]. Four recently published feasibility pilot studies of meaning-focused group psychotherapies for palliative care patients have included 5, 11, 11, and 16 patients each [40, 178-180].

Group therapy studies should include at least 2 groups of at least 4-6 members [135], so we plan to have at least 8 subjects complete the intervention. We expect to be able to enroll at least 6 subjects every 6 months.

Because the proposed study is a pilot focused on investigating safety and feasibility, power calculations for efficacy measures are not indicated. Pilot studies are often used to estimate values that are then utilized in power calculations for full-scale trials. Indeed, we will estimate effect size (ES) and the intraclass correlation coefficient (ICC) [132] for the intervention based on our preliminary efficacy results. Group psychotherapy trials generally require large sample sizes to demonstrate statistical significance in change in efficacy measures given the likely interdependence of clinical outcomes when interventions are delivered in groups [132, 133]. Thus, future full-scale trials can utilize our estimates to derive adequate, and likely large, sample sizes.

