## 8.2.2 Replacement Policy

Study subjects who have been assigned to a group and drop out prior to the first group session can be replaced by a new subject who will be assigned to the same group. Subjects who drop out after the first group therapy session will not be replaced.

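### The full-completion clause of the primary hypothesis (1.4) does not fit a sample size of 18 that was chosen to absorb dropout, and the plan states no other completion standard

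*Combined protocol and SAP*

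**What the plan says.** **The hypothesis.** Section 1.4 has one primary hypothesis. At least 18 subjects, in three groups of six, will enrol over 18 months, and "these subjects will complete all treatment and evaluation sessions and they will experience no treatment-emergent serious adverse events". Those subjects are the ones just enrolled, so the completion standard is 100%.

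**The sizing.** Section 3.2 says that "at least 18 patients will need to be enrolled given the high rate of drop outs seen in group psychotherapy studies". Section 8.2.1 puts a figure on it: "We estimate needing to enroll 18 subjects given attrition rates of up to 45% reported in trials of other group therapies". On completers, 3.2 says "We aim for, at minimum, 8 subjects (two groups of at least 4 subjects each) will complete the study", and 8.2.1 says "so we plan to have at least 8 subjects complete the intervention". Section 8.2.2 adds: "Subjects who drop out after the first group therapy session will not be replaced". In the background, 1.3 remarks that "Attrition rates of up to 50% are not uncommon among psychotherapy trials with palliative care patients".

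**Retention as a measure.** The abstract lists "Rate of Patient Retention (Sessions Attended and Follow-ups Completed" among the feasibility assessments. Sections 2.2.1, 7.1 and 8.1 also name retention. None of these gives a value that would count as success. Section 8.5, the primary analysis, does not list retention.

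**The concern.** Section 1.4 and the sizing sections use the same number, 18, with opposite expectations. In 3.2 and 8.2.1, 18 is needed because some subjects will leave. In 1.4, nobody leaves and nobody misses a session. If every subject were expected to complete, the stated reason for enrolling 18 would fall away.

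What is at stake is the conclusion on the primary objective, which is to demonstrate safety and feasibility. Section 1.4 is the only place that says what level of completion would show feasibility. If that level is almost out of reach, a well-retained pilot contradicts its own hypothesis, and no other stated benchmark exists for calling retention good or poor.

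**Working it through.** **Inputs from the plan.** Minimum enrolment 18 (1.4, 3.2, 8.2.1); maximum 36 (3.2, 8.2.1); groups of 6 (3.1); attrition of up to 45% in other trials (8.2.1); at least 8 completers (3.2, 8.2.1); no replacement after the first group session (3.2, 8.2.2).

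**Assumptions of this review.** Attrition values other than 45% are illustrative. Subjects drop out independently unless stated. The intraclass correlation (ICC) of 0.1 is assumed.

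**1. The plan's own 18.** Completers divided by (1 − attrition): 8 / 0.55 = 14.5, so 15 subjects. Rounded up to whole groups of six, this is 18. The plan gives no formula, and the rounding to groups is inferred from its group size. In the other direction, 18 × 0.55 = 9.9 expected completers, which covers the floor of 8. The chance of at least 8 completers out of 18 at 45% attrition is 87%. The sizing holds together.

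**2. The standard in 1.4.** With attrition d, P(all 18 complete) = (1 − d)^18. The ICC column uses a beta-binomial model with three groups of six.

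| Attrition d | P(all 18), independent | P(all 18), ICC 0.1 |
|---|---|---|
| 45% | 0.55^18 = 0.00002 (0.002%) | 0.0003 (0.03%) |
| 30% | 0.70^18 = 0.0016 (0.2%) | 0.7% |
| 20% | 0.80^18 = 1.8% | 4.3% |
| 10% | 0.90^18 = 15% | 22% |
| 5% | 0.95^18 = 40% | 48% |

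An 80% chance that all 18 complete needs attrition of 1 − 0.80^(1/18) = 1.2% per subject. If 36 enrol, the chance that all complete is 0.90^36 = 2.3% at 10% attrition and 0.95^36 = 16% at 5%.

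These figures count dropout only. Section 1.4 asks for every treatment and evaluation session, so a single missed session would also fail it. At each attrition rate the figures are therefore upper bounds.

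**3. Could the floor of 8 serve as the standard?** It is a fixed count while enrolment may run from 18 to 36. Eight of 18 is 44% retention; 8 of 36 is 22%. At 60% attrition, at least 8 completers would be reached 44% of the time with 18 enrolled and 99% of the time with 36. It works as a floor but not as a retention target.

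**4. How a proportional target would behave.** As an illustration, take 55%, the complement of the 45% ceiling. For 18 subjects, 0.55 × 18 = 9.9, so 10 are needed.

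| Attrition | P(at least 10 of 18), independent | ICC 0.1 |
|---|---|---|
| 30% | 94% | 90% |
| 45% | 58% | 57% |
| 60% | 13% | 19% |

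Such a target separates good from poor retention, somewhat less sharply when dropout clusters within groups.

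**5. Precision.** Exact two-sided 95% intervals: 17 of 18 retained, 73% to 99.9%. No serious adverse events in 18 gives an upper limit of 1 − 0.025^(1/18) = 18.5%; none in 36 gives 9.7%.

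**The case against.** The strongest reply is that 1.4 states a hope and 3.2 and 8.2.1 state a floor. Eighteen completers would satisfy both, so nothing is contradicted. The 8 comes from guidance on group design (two groups of at least four) and not from a forecast of retention. The 45% is the top of a range from other trials. The 50% in 1.3 describes palliative psychotherapy trials in general, in a passage that argues recruitment will be easier here. Safety and feasibility are described and not tested, no decision or stopping rule refers to 1.4, and 8.1 already promises descriptive statistics on retention. A result of 17 of 18 would simply be reported as 94%.

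Most of this stands. A reader might infer that the protocol contradicts itself, that 18 is miscalculated, or that the results would be biased or the trial formally declared a failure. The documents support none of these: a floor is compatible with full completion, the 18 can be reproduced, and the analysis is descriptive with no verdict attached.

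The reply does not remove the mismatch. The reason given for enrolling 18 is dropout, and even at 5% attrition, far below any figure the plan cites, the hypothesis would more often fail than hold. The commitment in 8.1 to describe retention supplies a number but no benchmark. The only benchmark is in 1.4.

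**Conclusion.** The point holds as an inconsistency between planning assumptions. It is neither a strict contradiction nor an arithmetic error, and the sample size should stay at 18. Under independent dropout, the completion clause would be met 0.002% of the time at the cited 45% ceiling and 40% of the time at an assumed 5%. An assumed ICC of 0.1 raises these to 0.03% and 48%, which leaves the conclusion unchanged. The consequence is limited to what the trial can claim about feasibility: no estimate is distorted, but losing one subject in 18 would contradict the primary hypothesis. It should be corrected, because the clause belongs to the primary hypothesis and the plan has no other completion standard.

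**What to change.** **Section 1.4.** Replace full completion with a retention target stated as a proportion of subjects who attend the first group session. Those who leave earlier may be replaced under 8.2.2, so this denominator avoids counting a replaced subject as a failure. Define completion from the abstract's own measure, sessions attended and follow-ups completed, and state how many of each are required. The sponsor should set the target to fit its own attrition assumption. The 55% used above only illustrates how a target behaves, and it would be missed 42% of the time with 18 subjects if attrition did reach 45%.

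**Sections 3.2 and 8.2.1.** Keep 8 as the floor for completers, and say that it is not the retention target.

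**Section 8.5.** List the retention rate already promised in 8.1, and report it and the serious adverse event rate with exact two-sided 95% confidence intervals.

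**Cost.** Wording only, with no added patients or procedures. The stated target becomes less ambitious.

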### Secondary

1. The difference in pre- and post-treatment mean scores of demoralization, complicated grief, depression, PTSD, shame, anxiety, quality of life, functional social support, post-traumatic growth, openness to experience, attachment security, mindfulness, global clinical impressions and ART medication adherence will trend toward significant improvement. These improvements will be sustained at 3-month follow-up.
2. The difference in pre- and post-psilocybin rates of change of group cohesion and group process will trend toward significant improvement.
3. Qualitative analyses of subject behavior and caregiver/important other reports will lead to greater understanding of the interpersonal mechanisms of action of psilocybin-assisted psychotherapy.

## 2 Objectives of the Study

### 2.1 Objectives

#### 2.1.1 Primary Objective

- To demonstrate the safety and feasibility of Psilocybin-Assisted Supportive-Expressive Group Psychotherapy (PA-SEGT) for demoralization in long-term AIDS survivors (LTAS).

